3.2 Adaptive Design

This study incorporates the use of an adaptive design. Study specific adaptive features and their limits are described in Table 3.

Adaptive features may be implemented only with the approval of the sponsor. Implementation of adaptive features affecting whole dose groups or cohorts, or the entire study, will be documented in a non-substantial amendment.

The exceptions to this are adaptive features **3 (limit I)**, **4 (limit I)** and **5 (limit I)**, which relate to individual subject safety. These may be implemented at the discretion of the investigator and recorded in that subject's source data.

Table 3. Adaptive protocol features.

Adaptive Study Design Areas	Features	Limits
Sentinel/subgroup dosing	1. Cohorts may be split into sub-groups.	I. A mandatory sentinel dosing strategy of dosing four subjects from treatment 1, and a minimum of two subjects each from treatments 2, 3 and 4 will be used. There will be a total of twelve subjects in the sentinel dosing. The remaining subjects can be dosed if safety and tolerability data up to 29 days post last dose is acceptable. II. The subjects in the sentinel group will all be dosed in parallel. If they are successfully dosed (i.e. it is deemed safe to dose the other subjects), the remaining 40 subjects may all be dosed at the same time, in parallel, or they may be divided into 2 or more dosing groups, with the groups being dosed on different days. Each dosing group would contain a minimum of two subjects from each of the 4 treatments, to maintain blinding and avoid bias.
Flexible Cohort Sizes	2. Withdrawn subjects can be replaced at the discretion of the sponsor and PI.	I. AR rules (Section 4.4)
Samples and Assessments (in-house duration and visit numbers)	3. The in-house stay or follow-up period may be prolonged or shortened if considered clinically necessary by the PI for individuals on a case-by-case basis.	I. A maximum extended in-house or follow-up period cannot be pre-defined as the extension will be as long as necessary to ensure the safety of the individual participant(s).
Samples and Assessments (safety)	4. Additional safety assessments may be performed on an individual subject if it is considered clinically necessary	I. For individuals, a maximum number of safety blood samples will be determined on a case-by-case basis and cannot be pre-defined as

Adaptive Study Design Areas	Features	Limits
	
by the PI for individuals on a case-by-case basis.
	
investigations will be performed as necessary to ensure the safety of the individual participants.
 
II. Study specific maximum blood volume will not be exceeded (Section 7.11).

	
5. Specialist referrals (e.g. to a cardiologist) may be made (and may include all relevant assessments and investigations) if it is considered clinically necessary by the PI or sponsor or SRC for individuals on a case-by-case basis
	
I. A maximum for individuals will be determined on a case-by-case basis and cannot be pre-defined as investigations will be performed as necessary to ensure the safety of the individual participants.

Samples and Assessments (PK)
	
6. Additional or fewer blood PK assessments may be taken in accordance with evolving data and dosing schedule. This includes those for the analysis of metabolites.
 
7. The timing of blood PK, and/or any potential exploratory assessments may be adjusted in accordance with evolving data and dosing schedule. This includes those for the analysis of metabolites.
 
8. General metabolite profiling beyond the metabolite specified in the objectives may be undertaken on selected or pooled PK samples and reported separately.
 
9. CYP2C8 genotype analysis may be performed, if PK data suggests that it is relevant (i.e. that a subject may be a CYP2C8 poor metaboliser).
	
I. Minimum: sufficient PK samples to establish full protocol specific plasma PK profile.
 
II. Study specific maximum blood volume will not be exceeded (Section 7.11).

Samples and Assessments (ECG assessments)
	
10. If PK sampling times are changed, then the matching ECG sampling times will be changed accordingly for exploratory QT/QTc analysis or intensive cardiac assessments.
 
11. If the meal times need to be changed, ECG times may also be changed to maintain the sampling schedule required to capture the food effect for the confirmation of assay sensitivity.
 
12. Telemetry data gathered during the study may be used in the exploratory analysis of drug
	
I. To confirm assay sensitivity, a minimum of four postprandial time points will be recorded in triplicate between 1-4h after the start of the meal.

Adaptive Study Design Areas	Features	Limits
	related QT/QTc interval changes.	
Screening	13. Screening assessments, including Holter ECG recordings performed at Richmond Pharmacology Ltd on volunteers screened (but not randomized) for another study can be used for this study to avoid unnecessary tests.	I. The assessments must meet protocol criteria (e.g. the method to be used). II. The assessments must be performed within the protocol defined screening window. III. The Holter ECG recordings are valid for a period of three months.

3.3 Rationale for study design, doses and control groups

This study will evaluate the tolerability and safety profile of the approved doses of ATV-PG and AQ when co-administered once daily for 3 days. The study is randomised and double blinded to minimise bias and includes placebo (unmatched) for ATV-PG and AQ to facilitate identification of effects related to treatment rather than the study procedures or situation.

3.3.1 Justification for the selected dose level

The approved adult malaria treatment dose of ATV-PG and the adult equivalent AQ dose that is used in children in combination with SP has been chosen for this study as these are the adult equivalent doses that will be used in SMC treatment of children.

The specified adult dose of ATV-PG is 1000 mg ATV + 400 mg PG once daily for 3 consecutive days [6] while the specified adult dose of AQ (for subjects over 13 years of age) is 600 - 612 mg once daily for 3 days (4 fold higher than the specified dose for 1-6-year olds) [7, 22].

3.3.2 Choice of subjects for study

Male and female subjects aged between 18 and 45 years considered healthy for their age are planned to be included in the study. The selection criteria are defined such that subjects selected for participation in the study are known to be free from any significant illness which potentially could confound the study results or put the subject at risk. Healthy subjects are also unlikely to require concomitant treatments which could interfere with the study drugs.

Considering that African population is at considerably higher risk of contracting malaria, this study will only recruit black subjects of sub-Saharan African origin (defined as subjects whose parents are black and are of sub-Saharan African origin).

3.3.3 Route and rate of administration

ATV-PG and AQ and placebos will be administered via the oral route.

3.3.4 Precautions to be applied for dosing between subjects within a cohort

A mandatory sentinel dosing strategy of dosing 12 subjects will be used to provide safety assessment in 4 subjects exposed to ATV-PG + AQ. The sentinel group will consist of 4 subjects from treatment 1, and a minimum of 2 subjects each from treatments 2, 3 and 4. Blinded safety data up to 29 days post last dose will be reviewed by a safety review committee (SRC) prior to dosing the remaining subjects.

If the sentinel group shows acceptable safety and tolerability, then the remaining subjects from all four Cohorts will be dosed.

The ratio of allocation to treatment group of the sentinel group has been chosen to ensure the safety of giving ATV+PG and AQ together, in a small number of subjects, while maintaining blinding.

The SRC will make a judgement (based on the minimum data requirements ([Table 4](#)) whether the drug administration to the remaining subjects can continue. See section [4.4](#) for Adverse Reaction (AR) rules.

3.3.5 Monitoring and communication of adverse events/reactions

AEs will be continuously monitored throughout the study from the signing of the informed consent form until the last follow up assessment. Each AE reported will be assessed by a trained Research Physician who will ensure that the event is dealt with as appropriate based on clinical need, study protocol, study operations manual and Richmond Pharmacology standard operating procedures (SOPs). AEs will be documented in the subjects' Case Report Forms (CRFs) and reviewed regularly by the Research Physicians and the investigator.

If any information relating to the study drugs in this study becomes available after the submission of a final protocol to the Competent Authority which may impact on the conduct of the study, including but not limited to the risk and benefit evaluations underpinning approvals and subject's consent, MMV shall notify RPL in writing as soon as practically possible and the parties will agree, in writing, what steps need to be taken if any.

3.3.6 Investigator Site Facilities and Personnel

This study will be conducted in a specialised early phase CPU with onsite resuscitation equipment and medication, in addition to access to an acute hospital with Critical Care facilities, thus ensuring direct access to equipment and staff for resuscitating and stabilising subjects in acute medical conditions and emergencies. The study is conducted by an experienced PI and well trained medical, nursing and technical staff with ample experience in the conduct of early phase clinical trials.

The study is designed to closely monitor, treat and communicate potential expected adverse reactions as well as potential unexpected adverse events.

3.3.7 Maximum Cohort Size

Following the reporting of an SAE in Cohort 1, it has been agreed between the SRC member to set the maximum cohort size at eight for all subsequent cohorts, with a minimum of one subject from each of the continuing treatment arms. A maximum of three subjects can be on the AQ + Malarone treatment arm within each cohort. This is to improve subject safety. Fewer subjects will ensure that all subjects can be assessed and managed (if required) properly, and everything can be documented properly.

Following the completion of dosing of the first 20 randomised subjects, Treatment 1 has been discontinued from further dosing in accordance with the Adverse Reaction (AR) rules in Section 4.4. Up to 24 further subjects will be included in the study, split in three cohorts of up to eight subjects.

The remaining three treatments will be re-randomised in such a way that across the whole study there will be still 12 subjects dosed with Treatment 2, 12 subjects with Treatment 3 and 12 Subjects with treatment 4. This is taking into account both the already dosed subjects with their originally randomised treatments and the newly randomised subjects yet to be included. Furthermore, within each cohort of up to eight subjects, each of the three treatments (2, 3, and

4) needs to be represented with a maximum of four and a minimum of one subject in the same cohort.

4. DECISION-MAKING, RULES AND LIMITS

4.1 Definitions

'Continuation' in the context of this protocol refers to either (1) continuing dosing in an individual subject or (2) continuing dosing in the study.

4.2 Rules and limits governing decision-making

The criteria and rules that will govern PI/SRC decisions are:

1. Minimum data requirements (Table 4).
2. Adverse reaction rules (section [4.4](#)).
3. Adaptive features and their limits (section [3.2](#)).

Table 4. Minimum data requirements to go from sentinel dosing to dosing remaining subjects.

STUDY PART			
Decision-making time point:	Person or body making the decision:	Minimum data to be looked at (in accordance with the CSP):	Method of documentation of decision and/or communication to sponsor (if applicable):
Continuation from the sentinel group to the remainder of the subjects in all cohorts	SRC	The SRC will review all available safety and tolerability data collected up to 29 days after first dose. All clinically significant findings will be taken into account by the SRC when determining whether the remaining subjects can be dosed as planned.	The SRC will document the decision on the dose continuation approval form.

4.3 Safety Review Committee

The SRC will consist of, as a minimum:

- Principal Investigator (RPL) or delegate
- MMV, Inc. Medical Advisor or delegate

Further internal or external experts such as a pharmacokineticist, and/or a statistician, may be consulted by the SRC as necessary. Any additional information, if required will be included in the study operations manual (SOM).

4.3.1 SRC Meeting

There is an option to have ad-hoc SRC meetings to discuss urgent issues should the need arise.

Prior to each SRC meeting, an interim safety report will be prepared, presenting the relevant safety and tolerability data. These will be signed by the investigator.

Initially the data will be reviewed blinded. If the SRC consider it necessary due to a safety concern, either individual subjects or the entire cohort may be unblinded to enable their decision-making. For non-emergency unblinding, before breaking the code, the potential decisions and actions should be determined and documented.

These decisions will be signed by one of the sponsor's representatives and by the investigator. For logistical reasons, the signature of the sponsor or investigator may be communicated via email.

The decision of the SRC will be taken in consensus between the members of the SRC. If consensus cannot be reached, then the most cautious approach will proceed.

 - i. Stop the AQ + Malarone treatment arm.
 - ii. Stop the Placebo + Malarone treatment arm.
 - iii. Continue the AQ + Placebo treatment arm**.
 - iv. Continue the Placebo + Placebo treatment arm.
 - d. Subject is on Placebo + Placebo
 - i. Temporarily halt the entire trial.
 - ii. Placebo to be investigated

*Assuming that no safety concerns are observed in subjects dosed with Malarone + placebo, the Sponsor may decide to terminate this arm for strategic reasons. If the combination treatment AQ + Malarone is terminated for safety reasons, then assessing Malarone monotherapy may be unnecessary as the safety profile is already established.

**By contrast, AQ may be used in combination with other anti-malarial medications in future trials and further safety/tolerability data (CNS & QTc effects in particular) with this drug in a well-controlled Phase1 study are needed, so obtaining data from the AQ monotherapy arm would still be beneficial.

4.4.1 General AR rules:

The general AR rules refer to all adverse reactions, excluding those relating to the liver and haematology and QT interval prolongation. There is a greater anticipation of adverse reactions relating to these latter categories, and CTCAE may not give clear enough guidance and grading may not be appropriate for this trial in healthy volunteers; therefore special study-specific rules have been created.

Individual AR rules:

IMP administration for an individual subject will be stopped if they experience any CTCAE grade III (or higher) AR, or a serious AR irrespective of severity/CTCAE grade.

IMP administration for an individual subject will be stopped if they experience any CTCAE grade I or II AR that raises safety concern.

Group AR rules:

IMP dosing will be suspended in all subjects, or potentially only in an affected cohort (if unblinding occurs), if either of the following occur:

- One subject experiences a severe (CTCAE grade III) AR
- One subject experiences a serious AR (irrespective of severity/CTCAE grade)

Dosing can only continue with a substantial amendment to the protocol which has been approved by the MHRA and ethics committee.

4.4.2 Special individual AR rules:

Dosing in an individual will be suspended if they experience any of the following:

- LFT elevation
 - ALT or AST value >3x ULN together with bilirubin increase >2x ULN.
 - ALT or AST value >8x ULN.
 - ALT or AST value >3x ULN, and symptomatic.
- Haematology
 - Hb drop to an absolute value of 8g/dL (80g/L) or lower.
 - Clinically significant drop in neutrophil count.*
 - Platelet count drop of >50% from baseline or absolute value <80.000/mm³ (Day -1 blood samples).
- QT interval prolongation
 - A prolongation of the uncorrected QT interval of greater than 500ms (using consistent, technically valid triplicate ECG).

*The special neutrophil rule has not been given a numerical value. This is because the subjects are of African origin and therefore a wide range of neutrophil values (including those that are outside the laboratory reference range. (i.e. Benign Ethnic Neutropenia and diurnal variation)) can be considered normal. These results will therefore be considered on a case by case basis.

4.4.3 Special group AR rules:

If one subject fulfils the special individual AR rules, and this could be reasonably attributed to one of the IMP medications, dosing for all subjects will be at least temporarily suspended and

a SRC meeting arranged. At this meeting, a decision will be made regarding the continuation of dosing in the remaining subjects.

If it is then confirmed that one subject fulfils Hy's Law criteria, dosing will be suspended in all subjects and can only continue with a substantial amendment to the protocol which has been approved by the MHRA and ethics committee.

If two or more subjects fulfil any of the other special individual AR rules, then dosing will be suspended in all subjects and can only continue if an SRC meeting is arranged (and a decision made that dosing can continue) and a substantial amendment is made to the protocol which has been approved by the MHRA and ethics committee.

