The CTCAE grading is now used in many clinical trials outside of oncology, where the terminology and grading may not always be accurate or applicable for non-cancer patients and healthy volunteers. In some cases it can be too limited in terms of available grades for specific diagnoses, and at other times it may lack the specificity to achieve appropriate grading for a listed diagnosis. CTCAE does not permit grading based on deviation from individual patients' baseline conditions, with few exceptions. There is also a significant overlap between listed severe Grade III and serious adverse events.

Standard toxicity terminology and grading according to NCI CTCAE, version 5.0 will therefore be used as a guide, rather than a rigid rule, to assess AEs and abnormal measurements.

Further details can be found in the SOM.

Causality:

The causality assessment of an AE to the IMP will be rated as follows by the investigator:

Reasonable Possibility: An AE which can be reasonably explained that the study drugs caused the AE by available facts (evidence) or arguments. For example, the occurrence of

the AE cannot be explained by other causative factors, but can be explained by pharmacological effect of the study drug such as:

- Temporal relationship to IMP exposure.
- Event is known to be associated with the IMP drug class.
- Event improved on discontinuation or dose reduction of IMP.
- Event reoccurred on re-challenge of IMP.
- Biological plausibility.
- Other (must be specified).

No Reasonable Possibility: An AE which cannot be reasonably explained by available facts (evidence) or arguments that the study drug caused the AE. For example, the occurrence of the AE can be explained by other causative factors, such as:

- Event attributed to concomitant medication (provide details of the concomitant medication).
- Event attributed to the concurrent disease (s) / condition(s) (provide details of the disease/condition).
- Event attributed to a non-investigational medicinal product (NIMP) (specify the NIMP).
- No reasonably temporal relationship associated with IMP administration.
- Event is expected in the study indication and/or target population.
- Negative de-challenge and/or negative re-challenge.
- Other (must be specified).

The investigator should also comment on the adverse event page of the Case Report Form whether an adverse event is not related to the study treatment but is related to study participation (e.g. study procedures, wash-out periods etc.).

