5.2 Laboratory Data

Clinical laboratory parameters (including blood chemistry, hematology, coagulation, urinalysis and other laboratory results) will be listed and abnormal parameters will be flagged as high (H) or low (L) according to reference ranges. Absolute (observed) values and changes from baseline (continuous variables) will be summarized for each parameter and scheduled time point by treatment group. The last lab value will be used for summary analysis if repeated measurements are made at any time point.

For summary statistics, a lab value with "<" will be replaced with a numeric value by removing the "<" sign. In the listings, the values will be displayed as originally reported by the laboratory.

Laboratory parameter values will be graded according to the Common Terminology Criteria for Adverse Events. Shift tables by treatment group will be produced for these laboratory parameters. These tables will summarize the number of subjects with each baseline grade relative to the normal ranges and changes to the worst highest grade assessed post-dose during the study.

The qualitative urinalysis data will be listed only.

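### SAP 5.2 counts subjects with neutrophil change by arm only through a CTCAE grade shift; it drops the protocol's count of clinically relevant laboratory values and has no count of falls from a subject's own baseline

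*Protocol*

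**What the plan says.** **Protocol, on neutrophils.** The footnote to 4.4.2 states that "The special neutrophil rule has not been given a numerical value", because in subjects of African origin "a wide range of neutrophil values (including those that are outside the laboratory reference range" can be considered normal. Results are judged case by case. Exclusion criterion 13 (5.4) bars subjects whose haemoglobin or platelets are outside the reference range. It does not do so for neutrophils, so a subject with a low count can enter unless it is judged clinically significant.

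**Protocol, on CTCAE.** Section 4.4.1, introducing the special rules for liver, haematology and QT, says "CTCAE may not give clear enough guidance and grading may not be appropriate for this trial in healthy volunteers". Section 8.2 says "CTCAE does not permit grading based on deviation from individual patients' baseline conditions, with few exceptions".

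**Protocol, on the planned count.** Section 10.3 has laboratory values flagged as clinically relevant or not, and summarises how many subjects have out-of-range and clinically relevant values. The primary endpoint (Protocol 2.2.1, SAP 2.2) includes the proportion of subjects with clinically relevant laboratory changes, haematology among them.

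**SAP 5.2.** "Laboratory parameter values will be graded according to the Common Terminology Criteria for Adverse Events". Shift tables by treatment group go from the baseline grade, relative to the normal ranges, to "changes to the worst highest grade assessed post-dose during the study". High and low flags appear in listings. In addition, "Absolute (observed) values and changes from baseline (continuous variables) will be summarized for each parameter and scheduled time point by treatment group". The Protocol 10.3 count is absent here, although SAP 5.6 keeps the same count for vital signs.

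**The concern.** Neutropenia and agranulocytosis are named amodiaquine risks (Protocol 1.2.2), and the primary endpoint for laboratory tests is a proportion of subjects. A grade shift anchored on the reference range suits neutrophils poorly here, for two reasons. A subject whose usual count lies near the lower limit can cross a cut-off through ordinary variation, and taking the worst of eight samples makes that likelier. A subject with a high baseline can lose half the count and still sit above the limit, at grade 0.

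The protocol gives relative-fall criteria for haemoglobin (8.2, AESI) and platelets (4.4.2) but none for neutrophils. The SAP adds no relative count, and it drops the one laboratory count that matched the endpoint. With 8 subjects on Treatment 1 and 12 planned on each other arm, a chance imbalance in low-baseline subjects could drive the shift table.

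**Working it through.** The plan states no figure to reproduce. The check has two parts.

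**1. Which by-arm outputs can contain neutrophils?**
- SAP 5.2 shift table: counts subjects, by CTCAE grade.
- SAP 5.2 change from baseline: by visit and arm, with mean, median and minimum (SAP 4). It does not count subjects or link one subject's visits.
- SAP 5.1 AESI and TEAE tables: count subjects by arm. A neutrophil drop judged clinically significant is a predefined AESI (Protocol 8.2), but it has no numerical definition.
- Protocol 10.3 laboratory count: not carried into SAP 5.2.

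So no subject count based on a stated fall from own baseline exists.

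**2. How does the shift table behave?**

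From the documents: one scheduled Day -1 baseline and eight scheduled post-dose haematology samples (Days 2, 3, 4, 8, 15, 22, 29 and 36; Protocol Table 1).

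Assumed, not in the documents: LLN 2.0 (or 1.8) x10^9/L; further grade cuts at 1.5, 1.0 and 0.5; lognormal values; within-subject CV 15 to 30%. With σ = √ln(1+CV²), CV 20% gives σ = 0.198.

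*Background shifts, no drug effect* (simulation, LLN 2.0, CV 20%):

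| Usual count | Worse worst-grade |
|---|---|
| 1.3 to 2.3 | 60 to 72% (38 to 77% over CV 15 to 30%) |
| 3.0 | 15% |
| 4.0 | about 0% |

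In a mixed population (geometric mean 2.5 to 4.5, between-subject CV 35%, LLN 1.8 or 2.0), 2 to 55% of untreated subjects shift. At geometric mean 3.0 the range is 15 to 43%, or 12 × 0.153 = 1.8 to 12 × 0.425 = 5.1 subjects in an arm of 12. At 4.5 it is 2 to 14%. A single post-dose visit would give 0.5 to 18%.

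*Missed falls.* A fall from 6.0 to an LLN of 2.0 is 1 − 2.0/6.0 = 67% and produces no grade. For a count halved at two visits (LLN 2.0, CV 20%):
- Usual count 5.0, halved to 2.5: P(below LLN at one visit) = Φ(ln(2.0/2.5)/0.198) = Φ(−1.13) = 0.130. At either visit: 1 − 0.870² = 24%. Over CV 15 to 30% this is 13 to 40%. With LLN 1.8 and CV 20% it is about 9%.
- Usual count 4.0, halved to 2.0: 1 − 0.5² = 75%.

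The table therefore detects halving well at low and middling counts and poorly at high ones.

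*A count of falls above 50% from own baseline.*
- False positives: at one visit Φ(ln 0.5/(0.198√2)) = Φ(−2.47) = 0.0067, so at most 8 × 0.0067 = 5.3% over eight visits. Simulation gives 4%, because the visits share one baseline (0.4% at CV 15%, 21% at CV 30%).
- Detection of a halving at two visits: the baseline must not be the smallest of three exchangeable values, so 1 − 1/3 = 67%, whatever the usual count.

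*A count of falls above 25%* flags 33%, 49% and about 64% of untreated subjects at CV 15%, 20% and 30%. In an arm of 12 that is about 4, 6 and 8 subjects. This band is too noisy to use.

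**The case against.** Much of the other side's case stands.

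- **Other output exists.** A reader might infer that the shift is the SAP's only by-arm neutrophil count, or that the SAP cannot show whether amodiaquine lowers neutrophils. Neither follows. Clinically significant drops are counted by arm as an AESI under SAP 5.1. Mean change against concurrent placebo, with the minimum, is tabulated by visit, and every value is listed. Large falls are missing from the shift count, not from the output.
- **CTCAE is not rejected.** The doubt in 4.4.1 explains the special dosing rules. Section 4.4 keeps CTCAE for standardised recording and reporting, and 8.2 keeps it as a guide for abnormal measurements. A descriptive shift table is compatible with that. What carries over to the analysis is the reasoning in the 4.4.2 footnote and in 8.2 about what the values and grades mean. The footnote also says only that such values can be normal, not that they are.
- **The placebo arm shows the background rate.** True, though with 12 subjects at most it does so imprecisely.
- **A threshold is a convention.** The protocol deliberately gave neutrophils no number, and a 50% fall does not define clinical relevance. The footnote also names diurnal variation, which affects a single baseline too. The relative count therefore supplements the clinically relevant count and cannot replace it.

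**Conclusion.** The point holds as a gap in SAP 5.2. Its only by-arm subject count from neutrophil data uses a scale that the protocol itself says mostly ignores own baseline, in a population where out-of-range values can be normal. The Protocol 10.3 count that matches the primary endpoint has been left out. Beyond judgement-based event tables and per-visit summaries, nothing counts subjects whose neutrophils fell from their own baseline.

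The direction of the bias is clear: background shifts near the LLN and missed halvings at high baselines. Its size is not known from the documents. It rests on the assumed LLN, grade cuts, variability and usual counts, and background shifts are few if most subjects sit well above the LLN. The study is exploratory and descriptive, so this affects how clearly a neutrophil signal can be read. It does not invalidate the safety analysis.

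**What to change.** In SAP 5.2:

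1. Restore the Protocol 10.3 count, by arm, of subjects with out-of-range and clinically relevant laboratory values, as SAP 5.6 does for vital signs.
2. Add, by arm, each subject's lowest post-dose neutrophil count as a percentage of the subject's own Day -1 baseline, with the number and proportion falling by more than 50%. This is the relative form that 4.4.2 already uses for platelets. Leave out a band for falls above 25%.
3. Label the neutrophil CTCAE shift as supportive.

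The cost is one or two tables from data already collected. The drawbacks are a conventional cut-off and a single noisy baseline, which could flag about a fifth of untreated subjects if within-subject CV is as high as 30%. This changes the analysis display only and no dosing or stopping rule.
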